Telemedicine has emerged as a valuable tool in diabetes management, especially through remote monitoring, communication platforms, and therapeutic adjustments. However, most studies involving telemedicine focus on outpatient or primary care contexts.

Given the severity of diabetes-related complications, the economic impact of hospitalizations, the persistently high readmission rates, and the need to strengthen medical knowledge for inpatient diabetes care, this study proposes a structured, telemedicine-based educational intervention. The objective is to evaluate its effectiveness in improving medical knowledge, insulin prescription quality, and the prevention and management of glycemic extremes during hospitalization.

2. Primary and Secondary Objectives

Primary objective:

To evaluate the impact of a structured educational intervention via telemedicine on internal medicine residents' knowledge regarding inpatient hyperglycemias.

Secondary objectives:

To assess the effect of the intervention on the quality of insulin prescriptions and capillary blood glucose monitoring.

To evaluate the effect on the occurrence of hypoglycemia and hyperglycemia during hospitalization.

To compare the length of hospital stay between the intervention and control groups.

3. Study Design

This was an open-label, multicenter, randomized clinical trial conducted at university hospitals located in southern Brazil. Internal medicine clinical teams were block-randomized using stratified allocation by center to ensure balance between groups.

The intervention group received a 30-minute online theoretical lecture on hospital hyperglycemia and participated in a 30-day telemedicine-based continuing education program delivered via a messaging platform. The control group continued standard clinical activities without any educational intervention.

Data collection occurred in two phases: a pre-post knowledge assessment using a validated questionnaire, and a retrospective chart review of hospitalized patients cared for by the participating teams.

4. Intervention

Residents in the intervention group received a 30-minute online theoretical lecture on inpatient hyperglycemia, followed by daily educational content for 30 days via a messaging application. Materials included short videos, texts, and clinical guidance on diabetes and hospital glycemic management.

The control group received no educational content and maintained routine clinical duties.

5. Inclusion and Exclusion Criteria

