Inclusion criteria:

Internal medicine residents assigned to clinical teams at participating hospitals.

Exclusion criteria:

Residents on leave during the intervention period.

Teams supervised by endocrinologists.

Residents who declined participation.

6. Outcome Measures (Primary and Secondary)

Primary outcome:

Change in medical knowledge on inpatient hyperglycemia, assessed through a validated questionnaire before and after the intervention.

Secondary outcomes:

Quality of glucose monitoring and insulin prescribing.

Incidence of hyperglycemia (>180 mg/dL) and hypoglycemia (<70 mg/dL).

Length of hospital stay

7. Sample Size Calculation

Based on previous data showing 46.44% accuracy in key knowledge items, and assuming an increase to 80% after the intervention, with 80% power and a 5% significance level, a minimum of 62 completed questionnaires (including both pre- and post-intervention assessments) was required.

8. Statistical Analysis Plan

Categorical variables were described as frequencies and percentages. Continuous variables were expressed as means and standard deviations or medians and interquartile ranges, based on normality (Shapiro-Wilk test).

Between-group comparisons were made using Student's t-test or the Mann-Whitney U test for continuous variables, depending on distribution. Categorical variables were analyzed using Pearson's chi-square test or Fisher's exact test, as appropriate. Logistic regression analysis was performed to identify independent predictors, including variables with clinical relevance or $p < 0.20$ in the univariate analysis. Statistical analyses were conducted using IBM SPSS Statistics for Windows, Version 29.0 (IBM Corp., Armonk, NY, USA). A two-sided p -value < 0.05 was considered statistically significant.

9. Ethical Considerations

All participating physicians provided informed consent. Data were collected with institutional authorization and approval by the local ethics committee. Confidentiality and privacy were strictly maintained for all participants and patient information.

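### Glucose is reported only as an undefined incidence above 180 or below 70 mg/dL; if read as ever/never per patient this discards much of the information, so define the unit and add a continuous summary

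*Combined protocol and SAP*

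**What the plan says.** Section 6 lists, among several unranked secondary outcomes, "Incidence of hyperglycemia (>180 mg/dL) and hypoglycemia (<70 mg/dL". It states no unit, denominator or time window. Section 2 gives the matching objective: "To evaluate the effect on the occurrence of hypoglycemia and hyperglycemia during hospitalization". The closing paragraph of Section 1 puts the aim as "the prevention and management of glycemic extremes during hospitalization", and Section 1 also names glucose variability among the disturbances linked to poor outcomes.

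The data come from "a retrospective chart review of hospitalized patients cared for by the participating teams" (Section 3). Section 2 includes "the quality of insulin prescriptions and capillary blood glucose monitoring" among the things assessed, so repeated readings per patient are a fair inference, but no testing frequency is given.

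Section 8 says "Between-group comparisons were made using Student's t-test or the Mann-Whitney U test for continuous variables, depending on distribution" and "Categorical variables were analyzed using Pearson's chi-square test or Fisher's exact test, as appropriate", and adds a logistic regression. It does not assign the glucose outcomes to any of these. No mean glucose, share of readings or variability measure appears in Section 6 or Section 8.

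**The concern.** An incidence, sent to chi-square, Fisher or logistic regression, most naturally becomes a yes/no per patient: was any reading above 180 mg/dL? That has three consequences.

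- **Severity and duration vanish.** A single reading of 185 and several days at 300 score the same.
- **The measure depends on how often the patient is tested.** With unchanged glucose, more readings mean more patients ever above 180. Monitoring quality is itself an outcome, so if the intervention increases testing, that alone pushes the incidence up in the intervention arm and could mask a benefit.
- **It saturates.** Once nearly everyone in both arms has crossed the line, a real fall in glucose hardly moves the result.

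At stake is how a null result on hyperglycaemia would be read. It could be taken to mean that better knowledge did not reach the patients, when the cause was the scale of analysis. Leaving the unit undefined also lets it be chosen after the results are seen.

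**Working it through.** **1. The plan's own figure.** Section 7 starts from "Based on previous data showing 46.44% accuracy in key knowledge items" and assumes a rise to 80%, with 80% power and 5% significance. With the arcsine formula, h = 2·arcsin√0.80 − 2·arcsin√0.4644 = 0.715, and n = 2·[(1.96 + 0.8416)/h]² = 30.7, so 31 per group and 62 in total, as stated. The pooled normal formula gives 32 per group, 64 in total. The figure reproduces, but it counts questionnaires. No number of patients and no power is given for any glucose outcome.

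**2. Loss from cutting one normal patient-level summary.** Efficiency relative to the uncut value is φ(c)²/[p(1−p)], where p is the proportion of controls above the cut and c = Φ⁻¹(p).

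| Controls above cut | Relative efficiency | Sample size multiplier |
|---|---|---|
| 50% | 0.64 | 1.57 |
| 80% | 0.49 | 2.04 |
| 90% | 0.34 | 2.92 |
| 95% | 0.22 | 4.47 |

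**3. Serial readings, uniform shift.** Every input here is an assumption, because the documents give none. A reading is M + noise, with M ~ N(μ, σb²) between patients and noise ~ N(0, σw²) within. There are m independent readings per patient, the intervention lowers μ by 10 mg/dL, and there is no team clustering. The grid is μ = 150, 170, 190; σb/σw = 30/50 or 40/40; m = 7, 14, 28 (18 combinations).

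- n per arm giving the patient mean 80% power: 2(1.96 + 0.8416)²(σb² + σw²/m)/10².
- Ever above 180: P = 1 − E[Φ((180 − M)/σw)^m].
- Share above 180: with p(M) = 1 − Φ((180 − M)/σw), its mean is E[p(M)] and its variance is Var[p(M)] + E[p(M)(1 − p(M))]/m.

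Worked case: μ = 170, SDs 40/40, m = 14. Then n = 2 × 7.849 × 1714.3/100 = 269.1, so 270 per arm. Ever above 180 is 0.899 in control and 0.854 with intervention. The null standard error is √(2 × 0.8765 × 0.1235/270) = 0.0283 and the alternative one is 0.0282. Power = Φ((0.045 − 1.96 × 0.0283)/0.0282), about 36%.

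| μ | σb/σw | m | n per arm | Ever >180, control / intervention | Power, ever | Power, share |
|---|---|---|---|---|---|---|
| 150 | 40/40 | 7 | 288 | 69% / 62% | 51% | 69% |
| 170 | 40/40 | 14 | 270 | 90% / 85% | 36% | 75% |
| 170 | 30/50 | 28 | 156 | 99% / 98% | 10% | 77% |
| 190 | 30/50 | 28 | 156 | 99.9% / 99.7% | 7% | 77% |

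Over the whole grid these formulas give 7% to 51% for ever above 180 and 68% to 77% for the share. Simulation of the same model gives about 7% to 55% and 65% to 79%. Different inputs (SDs 35/45, shift 15 mg/dL, means 150 to 180, 4 to 28 readings) give 12% to 50% and 62% to 78%.

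**4. Dependence on testing.** With μ = 170 and SDs 40/40, control incidence is 83% at 7 readings, 90% at 14 and about 94% at 28, with glucose unchanged.

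**5. A different kind of effect.** Keep the same n.

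- *Narrower swings only* (within-patient SD down 25%, mean unchanged): patient-mean power is 5%, ever above 180 has 11% to 91%, and the share, by the formulas above, only 6% to 34%. The chance of any reading below 70, 1 − E[{1 − Φ((70 − M)/σw)}^m], roughly halves. For example, it falls from 33% to 18% with μ = 170, SDs 40/40 and 28 readings.
- *Both* (10 mg/dL fall and within-patient SD down 15%): the mean has 80% to 82%, the share 69% to 96%, and ever above 180 has 14% to 96%, matching or beating the mean in 8 of the 18 combinations.

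**The case against.** The strongest reply has four parts.

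*The unit is not fixed.* The plan never says ever/never per patient, and Section 8 offers continuous as well as categorical tests. If incidence means the share of a patient's readings, the loss under a uniform shift is modest. This stands, and it is why the claim is conditional. It does not clear the plan, because an undefined unit permits the weakest version.

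*The threshold fits the objective.* Sections 1 and 2 speak of occurrence and of extremes, so an outcome defined by 180 and 70 mg/dL answers the stated question, and a mean answers a different one. This stands. It rules out replacing the threshold by the mean.

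*The comparison favours the mean by assuming a uniform shift.* This also stands. A reader might infer from step 3 that mean glucose always wins by a wide margin. Step 5 shows that it does not: highs and lows cancel in a mean, and an intervention that only narrows swings leaves the mean nothing to detect.

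*The ceiling is assumed.* No monitoring frequency, glucose distribution or patient eligibility is given; Section 5 covers residents only. The number of readings, and hence how near the ceiling the trial sits, is unknown. This stands as a limit on the size of the effect, not on its direction.

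**Conclusion.** The point holds in a conditional form. The documents show that the glucose outcomes have no unit, denominator or time window, and that no continuous summary is planned. If hyperglycaemia is analysed as ever/never per patient, information is lost. Under the stated assumptions and a uniform 10 mg/dL fall, power is about 7% to 55% where the patient mean has about 80% and the share of readings about 65% to 79%. These figures compare scales of analysis. They ignore team randomisation and are not the trial's power.

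A reader might go further and infer that a real improvement is likely to be missed. The documents do not support this: they give no patient number, glucose distribution or expected effect. Nor do they make hyperglycaemia the main patient-level outcome; it is one of several unranked secondary outcomes. The 180 and 70 mg/dL cuts are not errors in themselves. What is justified is a cheap improvement to a secondary outcome.

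**What to change.** In Sections 6 and 8:

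1. State the unit, denominator and time window of each glucose outcome.
2. Analyse hyperglycaemia per patient as the share of readings (or patient-days) above 180 mg/dL instead of ever/never. It stays a tested outcome, in line with the objective. The ever/never rate can be shown descriptively with the number of readings per patient by arm.
3. Add each patient's mean glucose during the stay (mean of daily means, mg/dL) as a further tested secondary outcome.
4. For each, report the between-arm difference with a 95% CI that accounts for the randomised teams.
5. Keep <70 mg/dL as a threshold event, because a mean hides rare lows, and read a lower mean only together with that result.

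The cost is wording and derived variables from values that should already be in the charts; no new patients are needed. The downside is one more secondary comparison. The share and the mean are both weak against an effect that only narrows swings, so a null on both would not exclude one; the hypoglycaemia result is then informative. The plan is written in the past tense, so anything added after data were seen must be labelled post hoc.

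### Section 7's 80% power is not established for intervention versus control: the unit of the 62 is unclear, no control-arm value is stated, and team randomisation is not allowed for

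*Combined protocol and SAP*

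**What the plan says.** All places are in the combined protocol and SAP.

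- **Section 7 (Sample Size Calculation)** starts from 46.44% accuracy in earlier data, "assuming an increase to 80% after the intervention", at 80% power and 5% significance, and concludes that "a minimum of 62 completed questionnaires (including both pre- and post-intervention assessments) was required". It names no test or formula, allocation ratio, control-arm value, team size or intracluster correlation (ICC).
- **Section 3 (Study Design)** sets the unit of randomisation: "Internal medicine clinical teams were block-randomized using stratified allocation by center to ensure balance between groups". It describes "a pre-post knowledge assessment using a validated questionnaire".
- **Section 4 (Intervention)** describes the comparator: "The control group received no educational content and maintained routine clinical duties".
- **Section 6 (Outcome Measures)** defines the primary outcome: "Change in medical knowledge on inpatient hyperglycemia, assessed through a validated questionnaire before and after the intervention".
- **Section 8 (Statistical Analysis Plan)** lists tests for individuals: "Between-group comparisons were made using Student's t-test or the Mann-Whitney U test for continuous variables, depending on distribution" and "Categorical variables were analyzed using Pearson's chi-square test or Fisher's exact test, as appropriate". It assigns none of them to the primary outcome, does not mention team, and sets a two-sided 5% level.

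**The concern.** A reader will take 80% as the planned power of the randomised primary comparison, and will weigh a null or imprecise result accordingly. Three gaps stand between Section 7 and that use.

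1. **Unit.** Pre and post questionnaires are both included in the 62. Read plainly, 31 residents with two forms each satisfy it. It may instead mean 62 residents.
2. **Contrast.** The rise is described over time. Reading 46.44% versus 80% as a comparison between arms requires controls to stay at 46.44%, which the text does not state.
3. **Clustering.** Teams are randomised, but neither the sample size nor the listed tests allow residents of one team to resemble each other.

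The scale is also open. Section 6 makes the outcome a change, and the plan does not say whether that change is a proportion correct on key items or a questionnaire score.

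**Working it through.** **Inputs.** From Section 7: p1 = 0.4644, p2 = 0.80, difference d = 0.3356, power 80%, alpha 5%. From Section 8: two-sided. Assumed here: 1:1 allocation and 62 as a total over both arms. Every control value other than 46.44%, and every team size, ICC, correlation and SD below, is an assumption.

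**Step 1. Reproduce the 62.** Pooled formula, with mean proportion 0.6322:

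n = [1.960·√(2·0.6322·0.3678) + 0.842·√(0.4644·0.5356 + 0.80·0.20)]² / 0.3356² = (1.3366 + 0.5381)² / 0.1126 = 31.2 per group.

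The arcsine formula gives 2(1.960 + 0.842)² / 0.7148² = 30.7, so 31 per group and 62 in total. The figure is sound for 31 + 31 independent observations. It fits 31 pre forms against 31 post forms as well as 31 residents per arm, so the arithmetic cannot settle the unit.

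**Step 2. Unit.** One post-intervention yes/no response per resident, controls at 46.44%, no clustering. Power = Φ[(d√n − 1.3366)/0.6393].

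- n = 31: Φ[(1.8685 − 1.3366)/0.6393] = Φ(0.832) = 79.7%.
- n = 15.5: Φ[(1.3213 − 1.3366)/0.6393] = Φ(−0.024) = 49.0%.

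Exact enumeration with the uncorrected chi-square test gives 80.3% at 31/31 and 53 to 56% at 15/16.

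**Step 3. Control-arm value.** Same model, intervention arm at 80%:

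| Control, post | Power, 31 per arm | Power, 15.5 per arm | n per arm for 80% |
|---|---|---|---|
| 46.44% | 79.7% | 49.0% | 31.2 |
| 50% | 70.7% | 41.3% | 38.5 |
| 55% | 55.8% | 31.1% | 53.9 |
| 60% | 40.2% | 22.3% | 81.2 |

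**Step 4. Clustering.** Replace n by n/DE, with DE = 1 + (m − 1)·ICC, and keep controls at 46.44%:

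| m, ICC | DE | 31 per arm | 15.5 per arm |
|---|---|---|---|
| 2, 0.01 | 1.01 | 79.3% | 48.6% |
| 4, 0.01 | 1.03 | 78.5% | 47.8% |
| 4, 0.05 | 1.15 | 73.7% | 43.5% |
| 4, 0.10 | 1.30 | 68.2% | 39.0% |
| 4, 0.20 | 1.60 | 58.7% | 32.4% |

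**Step 5. Yes/no change (Section 6), 31 per arm, controls unchanged, no clustering.** With pre-post correlation r, the variance per resident is 0.2487 + 0.16 − 2r·√(0.2487·0.16) in the intervention arm and 2·0.2487·(1 − r) in the control arm. Power = Φ[0.3356/√(sum/31) − 1.960].

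With the same r in both arms, the formula gives 50%, 65%, 79% and 94% at r = 0, 0.3, 0.5 and 0.7. The last two need a caveat. For one yes/no item moving from 46.44% to 80%, r in the intervention arm cannot exceed √[(0.4644·0.20)/(0.5356·0.80)] = 0.466. At that ceiling in both arms, the sum is 0.4888 and power is 76%. The control arm has no such ceiling: with 0.466 in the intervention arm and 0.7 in the control arm, the sum is 0.3722 and power is 86%. Power can therefore fall on either side of 80%.

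**Step 6. Change score, t-test, no clustering (noncentral t).** Largest change-score SD that keeps 80% power:

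| Net difference | 15.5 per arm | 31 per arm |
|---|---|---|
| 33.56 points | 32.2 | 46.4 |
| 20 points (assumed) | 19.2 | 27.7 |

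**The case against.** **The 46.44% is the natural control value.** Controls were taught nothing, and 31 + 31 fits a comparison of arms. This is a fair reading, and under it the contrast gap is only an unstated assumption. It still has to be written down, and it settles neither the unit nor the clustering.

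**The low figures come from one model.** They treat each resident as giving a single yes/no response. Section 7 speaks of several items and Section 6 of a change, so a score analysis is equally possible. At 15.5 per arm and a 33.56-point net difference, it has about 95% power at an SD of 25 and 85% at an SD of 30. This stands: no SD is given, so neither scale can be preferred.

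**Fisher's exact test matters little at 31/31.** It would give 72% there if always used. Section 8 allows either test, and under the common rule of switching when an expected count is below 5 (an assumption; the plan states no rule) power stays at 80.3%. At 15/16 that rule gives about 48 to 52%. This stands.

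**Clustering may be trivial.** With 2 residents per team and ICC 0.01 the loss is under one point. What stands is that no allowance is stated.

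**The trial is described in the past tense.** Restating power does not change the estimate. This stands, and it is why the interval matters more than the power figure.

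A reader might infer that 62 is miscalculated, or that the trial is underpowered. Step 1 rules out the former. The latter would need a unit, scale, SD, correlation, team size and ICC that the documents do not give. Nor can one say that 80% holds only when 62 means residents, controls stay still, clustering is negligible and an uncorrected chi-square test is used. Those conditions describe a post-only comparison, and Steps 5 and 6 show that a change outcome can fall below 80% with them met or exceed it without them.

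**Conclusion.** The concern holds as a statement that 80% power is not established for the randomised comparison. Confidence is high for the three omissions and does not extend to any particular shortfall.

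- On the unit alone, the same sentence allows about 80% or about 49%, for a single post-intervention yes/no response with controls at 46.44% and no clustering.
- An assumed 4 residents per team with ICC 0.01 to 0.20 lowers these to about 78 to 59% or 48 to 32%. The true clustering loss is not established.
- For the Section 6 change outcome, power depends on a correlation or SD that the documents lack, and may lie above or below 80%.

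The point should be fixed because it affects how the primary result is read, and the repair is small.

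**What to change.** **Section 7, in a dated clarification:**

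1. Say whether 62 counts residents or forms, and restate it as residents per arm.
2. Name the contrast, the formula used and the control-arm assumption.
3. State that no allowance was made for team randomisation.
4. Qualify the 80% rather than withdraw it: print it only with those conditions. Beside it, give a labelled range on the scale and test of the primary outcome, varying the control-arm value and the change SD or pre-post correlation, with a design effect 1 + (m − 1)·ICC from the actual team sizes. Mark assumed inputs as such.

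**Section 8:** name the scale of the primary outcome, and estimate the between-arm difference in change with a standard error and confidence interval that account for team.

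**Cost:** one rewritten paragraph, a small table and one added analysis sentence. The sponsor must supply the formula, the unit and the team sizes, and ranges for the remaining inputs. The stated power may become less favourable and the interval may be wider. No added residents are needed.

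### Where a t-test is used, name Welch's version: Student's pooled standard error is wrong if arm sizes and spread both differ, and the design secures neither condition

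*Combined protocol and SAP*

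**What the plan says.** Section 8 gives one rule for continuous outcomes: "Between-group comparisons were made using Student's t-test", with the Mann-Whitney test as the alternative and the choice made on distribution. It names no unequal-variance version, no variance check and no rule for which line of the SPSS output is reported. It does not mention confidence intervals.

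Section 3 sets the unit of allocation: "Internal medicine clinical teams were block-randomized using stratified allocation by center to ensure balance between groups". Section 5 then applies exclusions to individual residents (leave, refusal) as well as to some teams.

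Section 6 defines the primary outcome as "Change in medical knowledge on inpatient hyperglycemia, assessed through a validated questionnaire before and after the intervention". One arm is trained and the other receives nothing.

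The documents state no arm sizes, no SDs, no team sizes and no number of teams.

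**The concern.** The pooled variance in Student's test gives the right standard error if the arms are equal in size or equal in spread. The plan guarantees neither.

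- **Arm size.** Blocking within center controls how many teams go to each arm. Resident numbers depend on team size, on individual exclusions and on who completes both questionnaires. In an open-label study, completion may also differ by arm.
- **Spread.** Change in the trained arm mixes varied uptake with retest noise, while change in the control arm is mostly retest noise. A ceiling near the top of the questionnaire could instead narrow the trained arm. The direction is unknown, but a common SD is an assumption that the plan does not state.

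If both conditions fail and the smaller arm is the more variable, p-values are too small and an interval for the difference is too narrow. If the larger arm is the more variable, intervals are too wide and power is lost.

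**Working it through.** **1. The plan's own figure.** Section 7 starts "Based on previous data showing 46.44% accuracy in key knowledge items", continues "assuming an increase to 80% after the intervention", "with 80% power and a 5% significance level", and arrives at 62. The two-sided arcsine formula for two proportions, n per arm = 2(1.960 + 0.842)²/h² with h = 2·arcsin√0.80 − 2·arcsin√0.4644 = 0.715, gives 30.7. That rounds to 31 per arm, 62 in total. The pooled two-proportion formula gives 32 per arm, 64 in total. So 62 is reproduced. It was sized on proportions, and the choice of t-test does not alter it.

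**2. Inputs.** From the documents: a total of 62, read here as 62 residents with a pre and a post score each, and a two-sided 5% level. Assumed, because the documents give none: the split between arms, the SD ratio (trained/control), normal scores and, at this step, independent residents.

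**3. Ratio of Student's standard error to the true one.** With control SD 1 and trained SD r:

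- Student's variance: [((n₁ − 1)r² + (n₂ − 1))/(n₁ + n₂ − 2)] × (1/n₁ + 1/n₂)
- True variance: r²/n₁ + 1/n₂

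If r = 1 the two agree for any split. If n₁ = n₂ = n, both equal (r² + 1)/n for any r. Both conditions must therefore fail before any error arises.

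Trained 40, control 22, r = 0.5:

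- Student: (39 × 0.25 + 21)/60 × (1/40 + 1/22) = 0.5125 × 0.07045 = 0.0361
- True: 0.25/40 + 1/22 = 0.0517
- SE ratio: √(0.0361/0.0517) = 0.84 (too small)

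Trained 22, control 40, r = 0.5:

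- Student: (21 × 0.25 + 39)/60 × 0.07045 = 0.7375 × 0.07045 = 0.0520
- True: 0.25/22 + 1/40 = 0.0364
- SE ratio: 1.20 (too large)

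**4. Error rate, 40,000 simulated trials per row, equal means.** The figure is also the non-coverage of the 95% interval at any true difference, because adding a constant to one arm does not change the distribution of the estimate about its target.

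| Trained/control | SD ratio | SE ratio | Student | Welch |
|---|---|---|---|---|
| 31/31 | 0.5 | 1.00 | 5.2% | 5.0% |
| 40/22 | 1 | 1.00 | 5.0% | 4.9% |
| 34/28 | 0.75 | 0.97 | 5.6% | 4.9% |
| 34/28 | 0.5 | 0.94 | 6.5% | 5.0% |
| 40/22 | 0.75 | 0.92 | 7.3% | 5.1% |
| 40/22 | 0.5 | 0.84 | 10.4% | 5.0% |
| 22/40 | 0.75 | 1.09 | 3.4% | 5.0% |
| 22/40 | 0.5 | 1.20 | 2.0% | 5.1% |

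The ratio hardly depends on the total. If 62 counted pre and post sheets separately, there would be 31 residents. A 20/11 split with r = 0.5 then gives √{[(19 × 0.25 + 10)/29 × (1/20 + 1/11)]/(0.25/20 + 1/11)} = 0.83.

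**5. Price of Welch when variances are equal.** At an assumed effect of 0.75 SD, power is 82.7% (Student) against 82.6% (Welch) at 31/31, and 79.3% against 78.8% at 40/22.

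**6. What Welch does not do.** With 31/31, equal SDs and residents correlated within teams (team size and ICC assumed), both tests reject 8.6% of the time for teams of 4 with ICC 0.10, and both 16.6% for teams of 6 with ICC 0.20.

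**The case against.** The strongest reply has four parts.

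- **If training affects nobody, randomization gives both arms the same expected distribution.** The variances then agree and this mechanism cannot inflate the error rate. That stands. A false-positive rate of 10% would need training that changes the spread a great deal and the mean not at all. The practical harm is to interval coverage and power when training has some effect, and the plan promises no interval.
- **The inputs are assumed.** That stands too. Blocking within center aims at balance, nothing in the documents points to 40/22, and at 34/28 with an SD ratio of 0.75 the excess is 0.6 percentage points. In the reverse direction the test is conservative.
- **The t-test is one branch.** Scores judged non-normal go to Mann-Whitney, and Section 7 sizes the trial on proportions, so the plan does not settle which test the primary outcome receives. The wording also does not say in terms that the pooled line of the output is reported, although that is the ordinary meaning of the named test. The point therefore reaches only outcomes that go to a t-test.
- **Clustering matters more.** Step 6 bears this out, and a cluster-adjusted analysis would displace the simple t-test. The question of one variance or two would still arise in its replacement.

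These replies reduce the point to a conditional one. They do not supply a reason to prefer the pooled version.

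**Conclusion.** The point holds as a conditional, minor one. On the t-test branch the plan names a method whose standard error depends on equal arm sizes or equal spread, and the design secures neither. The illustrative range for Student's error or non-coverage runs from about 2% to about 10%, against about 5% for Welch. It rests on assumed splits and SD ratios, normal scores, 62 residents and independence between residents.

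A reader might infer three stronger things, none of which the documents support:

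- **That unequal arm sizes alone spoil the test.** They do not: 5.0% at 40/22 with equal SDs.
- **That this trial's primary test runs at 10%.** No arm sizes or SDs are given, the direction is unknown, and the primary test is not identified.
- **That Welch answers the allocation of whole teams.** It still treats residents as independent. Team allocation matters to this point only because it leaves the number of residents per arm uncontrolled.

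**What to change.** In Section 8, state that where a t-test is used it is Welch's unequal-variance comparison, reported with the mean difference and its 95% confidence interval. In SPSS this is the 'equal variances not assumed' row. State also that no Levene pre-test decides between the rows, so that the choice does not depend on the data.

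Treat team allocation as a separate and larger change. If it leads to a team-level analysis, use Welch on the team summaries. If it leads to a mixed model, allow a separate residual variance per arm. With few teams either option has few degrees of freedom, and the documents do not give the number of teams, so check feasibility first.

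The cost is one phrase in Section 8, no change to the 62, and at most about half a percentage point of power in the equal-variance cases above. The document is written in the past tense. If the t-tests have already been run, SPSS has printed the needed row and no new data are required, but the report should say that the choice was made afterwards.
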